If safety data suggest increase benefit combined with increased harm for the 60 mg dose compared to the 45 mg dose, we will discuss potential options with the DSMB. For example we may see increased rate of re-arrest with the 60 mg dose, but a higher rate of survival to hospital admission or to discharge. In this case, an argument to use the 60 mg dose would be made.

Finally if both the 45 and 60 mg dose demonstrate an adverse safety signal then we will abandon plans for a phase 3 trial.

PHASE 2. EXAMINE THE SAFETY AND EFFICACY OF FIELD ADMINISTRATION OF SODIUM NITRITE DURING RESUSCITATION OF OUT-OF-HOSPITAL CARDIAC ARREST

The hemodynamic effects of the optimal dose of IV nitrite administered in patients with cardiac arrest are unknown. A significant negative hemodynamic effect from nitrite would decrease the proportion of patients admitted to the hospital, increase rate of re-arrest, or increase the need for vasopressor support in the field. In Seattle/King County, typically 40% of out-of-hospital cardiac arrest patients attended to by paramedics have ROSC and are admitted to the hospital. In this study, 1500 patients

with out-of-hospital cardiac arrest who are undergoing resuscitation by paramedics will be randomized to receive placebo (n=500) or 45 mg IV (n=500) or 60 mg dose (n=500) of sodium nitrite. We will have 80% power to detect an absolute increase in hospital admission rate of 8% (1-sided .05 level test for each of the two comparisons (45 mg vs placebo and 60 mg vs placebo, no adjustment for multiple comparisons), with a hospital admission rate of 40% in the placebo group and with one interim analysis and stopping only for potential futility and/or harm). We will examine the proportion of patients who survive to discharge as a secondary measure of efficacy.

Overview of Study design and definitions

In this phase 2 study, a total of 1500 patients with out-of-hospital cardiac arrest in Seattle/King County will be enrolled. This will be a randomized clinical trial and patients will receive either two different doses of IV sodium nitrite (45 mg or 60 mg) or placebo during resuscitation in the field by paramedics. The primary safety outcome will be proportion of patients surviving to hospital admission and primary efficacy outcome will be survival to discharge.

Patients will be eligible for both studies if:

1. Intravenous access/intraosseous access
2. Cardiac arrest, either VF or non-VF patients receiving ACLS by Seattle Medic One paramedics.

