The incidence of adverse events will be recorded for all patients in the safety population and presented by treatment arm (60 mg / 45 mg / placebo) to the DSMB for their review during the conduct of the study, as well as summarized and compared across treatment arms in the final report of study results. Assessment of the statistical significance of differences in the incidence of safety endpoints plays a lesser role, due to the need to be cautious in the introduction of new treatments in a human population. Hence, emphasis is placed on the presentation of results, with statistical tests provided for guidance on the precision of estimates as indicated. Specific measures that may reflect the safety of nitrite include:

1. Delay of Treatment. The process of initiating nitrite (or placebo) could delay treatment and/or potentially cause harm in patients other than those for whom the intervention is beneficial. The distribution of time from EMS arrival on scene to patient arrival at hospital will be described using mean, standard deviation, minimum, 25th, 50th, and 75th percentiles, and maximum. These data will be compared to historical data to determine whether this study affected treatment times. When indicated, statistical tests comparing the distribution of times will be affected using the t test, which allows for unequal variances.

2. Complications of Treatment The incidence of any Unexpected adverse death/events UADE will be reported by treatment arm and compared as indicated using Pearson's chi squared or unconditional exact test statistic (if expected numbers for any cells are small) and trend test across placebo, 45 mg and 60 mg.

3. Serious Adverse Events The incidence of each serious adverse event, along with other major adverse medical or surgical outcomes identified during review of hospital records, will be tabulated by treatment arm and compared when indicated using Pearson's chi squared or unconditional exact test (if expected numbers for any cells are small) and trend test across placebo, 45 mg and 60 mg groups). In order to

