facilitate the identification of differences in rates of such events that might be due to greater survival to hospital admission and/or hospital discharge on one of the treatment arms, the incidence of any of the above specific events and/or death (either pre-hospital or during hospitalization) will be reported using all patients randomized to the arm as the denominator. While the study is ongoing, these data will only be available to the unblinded statisticians and the DSMB.

Sample Size and Monitoring plan for Phase 2.

There are no preliminary human data available for this study. This study will provide such data. In a rodent model of cardiac arrest in which sodium nitrite is administered at the time of resuscitation, the intervention resulted in a 25% absolute increase in survival (50% to 75%)¹¹, however, this effect size is probably overly optimistic.

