Regarding the primary hypotheses: This study will have 80% power to detect an absolute increase in hospital admission rate of 8.0% (1-sided 0.05 level test, with a hospital admission rate of 40% in the placebo group) for each of the treatment arms (45 mg or 60 mg) when compared to placebo (without adjustment for multiple comparisons). We believe that not adjusting for multiple comparisons is justifiable for this early phase exploratory study, because the major Type I error is to discontinue any further investigation of a new treatment. Figure 1 provides sensitivity analyses to the power calculations by providing power estimates for a range of effect sizes and three rates of survival to hospital admission (30%, 40% and 50%) (applicable to each of the two primary comparisons). The study will be monitored by the DSMB at least four times, after about one quarter, about half and about three quarters of patients are enrolled and at the end of the study. Because of the size of the study, a single interim formal analysis will be performed (in addition to the final analysis). Of note, the DSMB can recommend stopping of the trial if there are concerns apparent at any of the reviews even if no formal interim analysis is scheduled. A one-sided boundary was chosen such that the study will only stop for futility and/or harm if the maximum likelihood estimate of the differences in proportions of survival to hospital admission is -0.001 or less (i.e. a slightly lower proportion of patients in the treatment arm survives to hospital admission than in the control arm after 500 patients have been enrolled). At the interim analysis no consideration will be made regarding stopping the study early for superiority.

[figure not shown]

Figure 1: Power for a study with 30%, 40% or 50% survival to hospital admission for effect sizes ranging from 6% to 10%.

Regarding the secondary hypothesis of survival to hospital discharge: The study will have more than 80% power to detect an absolute increase in survival to hospital discharge or 6.7% (1-sided 0.05 level test) in each of the two treatment groups with a survival to hospital discharge rate of 20% in the placebo group. Power estimates were obtained using SeqTrial (S-Plus).

Potential outcomes after safety analysis: (stopping rules)

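### The event-or-death report cannot separate a survival artefact from real toxicity when a dose also improves survival

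*Combined protocol and SAP*

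**What the plan says.** In the combined protocol and SAP, under Analyses, 3. Safety Analysis, item 3 (Serious Adverse Events), there are two reports.

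- The incidence of each serious adverse event, without death, "will be tabulated by treatment arm and compared when indicated using Pearson's chi squared or unconditional exact test", with a trend test across the three arms.
- A second report, meant to "facilitate the identification of differences in rates of such events that might be due to greater survival to hospital admission and/or hospital discharge". Its measure is given as: "the incidence of any of the above specific events and/or death (either pre-hospital or during hospitalization) will be reported using all patients randomized". Everyone allocated to an arm is in that arm's denominator.

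The plan has no event rate among admitted patients, no analysis that treats death as a competing outcome, and no statement of how the two reports are to be read together.

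The survival figures that fix the size of the composite come from Sample Size and Monitoring plan for Phase 2. For discharge the plan claims "more than 80% power to detect an absolute increase in survival to hospital discharge or 6.7% (1-sided 0.05 level test"), and the placebo value it starts from is given in the words "with a survival to hospital discharge rate of 20% in the placebo group". For admission it uses a "1-sided 0.05 level test, with a hospital admission rate of 40% in the placebo group" and a target increase of 8.0 points.

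**The concern.** In-hospital events can occur only in patients who reach hospital, so a dose that gets more patients admitted will raise the crude event rate even if it is not toxic. The second report is the plan's answer to that problem, and the only one it offers.

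Merging the event with death defeats the purpose. A patient who dies counts whether or not the event occurred, so an event changes the composite only in a patient discharged alive. Each point of survival gained takes a death out of the composite. A harmless dose that saves lives lowers it. A toxic dose that saves lives can also lower it, or leave it flat. The two cases that the report is meant to separate then point the same way.

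This happens at the survival effects the trial is powered to find. The Introduction also foresees a dose that brings both more benefit and more harm, and refers that case to discussion with the DSMB. The DSMB would want a table that can tell the two explanations apart.

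**Working it through.** **Inputs from the plan.** Arm sizes are "placebo (n=500) or 45 mg IV (n=500) or 60 mg dose (n=500) of sodium nitrite". Admission is 40% on placebo and 48% at the target effect. Discharge alive is 20% on placebo and 20 + 6.7 = 26.7% at the target effect.

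**Assumption.** The plan gives no event rate. I take an event risk of 20% per admitted patient on placebo, independent of later death, and vary it below.

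**The plan's own figures.** A two-proportion calculation (500 per arm, one-sided 0.05) gives 81.8% power for 40% vs 48% with no interim look. Simulating the stated boundary (difference of -0.001 or less) at 167 per arm gives 79.8%, against the stated 80%. For 20% vs 26.7% it gives 80.6% with no interim look, in line with the stated more than 80%. The survival inputs are therefore the plan's working values.

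**The composite.** Let s be the proportion discharged alive and q the event risk in those discharged alive. Then C = (1 - s) + s × q.

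- Placebo: 0.80 + 0.20 × 0.20 = 84.0%.
- Dose at the target survival effect: 0.733 + 0.267 × q.
- Events per randomised patient: 0.40 × 0.20 = 8.0% on placebo and 0.48 × q on the dose.

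| Event risk on dose | Events per randomised patient (placebo 8.0%) | Composite (placebo 84.0%) | Difference in composite, points | Chance that the observed composite shows no excess |
|---|---|---|---|---|
| 20% (no toxicity) | 9.6% | 78.6% | -5.4 | 98.5% |
| 30% | 14.4% | 81.3% | -2.7 | 87% |
| 40% | 19.2% | 84.0% | 0.0 | 50% |
| 50% | 24.0% | 86.7% | +2.7 | 12% |

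The last column uses a normal approximation with SE = √[C0(1 - C0)/500 + C1(1 - C1)/500].

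**How large a rise can be masked.** The composite shows no excess while q1 ≤ [(s1 - s0) + s0 × q0] / s1. At q0 = 20% and the full gain, this is (0.067 + 0.040)/0.267 = 40.1%.

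| Placebo risk q0 | Limit at 26.7% discharged alive | Limit at 22% discharged alive |
|---|---|---|
| 5% | 28.8% (5.8-fold) | 13.6% (2.7-fold) |
| 10% | 32.6% (3.3-fold) | 18.2% (1.8-fold) |
| 20% | 40.1% (2.0-fold) | 27.3% (1.4-fold) |
| 30% | 47.6% (1.6-fold) | 36.4% (1.2-fold) |

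This limit concerns risk in patients discharged alive and does not need independence. Independence is needed only to link it to the crude rates in the first table.

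**What a split table would show**, as a percentage of all randomised, under the same assumptions:

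| Outcome | Placebo, risk 20% | Dose, risk 20% | Dose, risk 30% | Dose, risk 40% |
|---|---|---|---|---|
| Died before admission | 60.0 | 52.0 | 52.0 | 52.0 |
| Admitted, event, died | 4.0 | 4.3 | 6.4 | 8.5 |
| Admitted, event, discharged alive | 4.0 | 5.3 | 8.0 | 10.7 |
| Admitted, no event, died | 16.0 | 17.0 | 14.9 | 12.8 |
| Admitted, no event, discharged alive | 16.0 | 21.4 | 18.7 | 16.0 |

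Each cell is the product of the stated rates; for example, 0.267 × 0.30 = 8.0%. The scenarios that overlap in the composite now separate. Event risk among the admitted is 8.0/40 = 20% on placebo, against 9.6/48 = 20%, 14.4/48 = 30% and 19.2/48 = 40% on the dose.

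**The case against.** A reader might infer that a toxic excess would be hidden, dismissed as a survival artefact, and the dose judged safe. The documents do not support that.

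- **The excess stays visible.** The event-only table would show 8.0% vs 19.2% (40 vs 96 events per 500) for a doubled risk. For 8.0% vs 14.4% it has about 90% power at a two-sided 0.05 level. Only attribution is affected.
- **No reading rule exists.** Nothing says that a flat composite means the excess is explained by survival. The Safety Analysis gives significance tests a smaller role than presentation, and the stopping-rules section leaves arm decisions to scientific judgement.
- **The answer can be worked out from other outputs.** Admission is the primary outcome and is reported by arm, so 40/200 vs 96/240 follows by division. Subtracting deaths from the composite gives patients alive with the event: 84.0 - 80.0 = 4.0% vs 84.0 - 73.3 = 10.7%. This is true, but the plan does not ask for either step.
- **Cancellation is conditional.** It needs a survival gain, and larger excesses still show. The 20% risk is assumed. Independence is doubtful for shock, which the Safety Outcomes section links to survival.
- **Not every safety measure is affected in this way.** Survival to admission is named as the primary safety outcome. Re-arrest and field vasopressor use can occur before admission, so the premise that events require hospital arrival does not cover them.
- **The wording is loose.** It could mean events and deaths shown side by side. The merged reading is the natural one, but the text does not settle it.
- **The composite has a merit.** It preserves the randomised comparison, which an admitted-only rate does not.

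These points narrow the concern to attribution. They do not make the merged measure fit for the purpose the plan gives it.

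**Conclusion.** The point holds as a cheap improvement. On its merged reading, the one measure chosen to help attribute adverse-event differences to survival cannot do so when a dose also improves survival. At the planned discharge gain and an assumed 20% placebo event risk, no toxicity and a rise to 30% both lower the composite, and a doubling leaves it unchanged. Over assumed placebo risks of 5% to 30%, the rise that can be masked runs from about 5.8-fold to 1.6-fold. With a gain of only 2 points it runs from about 2.7-fold to 1.2-fold.

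The conclusion rests on the plan's 20% discharge survival, a survival gain on the dose, an event rate that the plan does not give, and the merged reading. Misreading an excess as a survival artefact is a risk left open by the missing guidance; it is not a rule in the plan.

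**What to change.** In item 3 of the Safety Analysis:

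1. State whether the measure is merged. If it is, keep it only as a descriptive net-outcome line.
2. For attribution, report by arm over all randomised patients: died before admission; admitted with the event (died / discharged alive); admitted without the event (died / discharged alive). Show death separately, and give each dose's difference from placebo with a confidence interval.
3. Tabulate pre-admission events, such as re-arrest, on their own.
4. Add the event risk among admitted patients, labelled as conditional on a post-randomisation state. With about 200 vs 240 admitted, it would have about 67% power for 20% vs 30% and over 99% for 20% vs 40% (two-sided 0.05).
5. Say how these lines are to be read together, and use the same table in the DSMB reports and the final report.

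The cost is one paragraph and one table shell, using admission, event and discharge data already collected. The drawback is that the admitted-only risk is not a randomised comparison. No change to any stopping or dose rule is proposed.
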